### **9.7.1.4 Subjects Lost to Follow Up**

All reasonable efforts (at least 3 contact attempts via phone/email, or registered letters) will be made to obtain complete data for all subjects, before they are considered lost to follow-up. Missing observations may occur due to subjects who are lost to follow-up or demonstrate noncompliance with the required assessments.

### **9.7.1.5 Data Collection & Follow-Up for Discontinued/Withdrawn Subjects**

All subjects enrolled in the study are considered eligible for follow-up and will be required to adhere to the assessment schedule found in Table 9-2. Subjects may withdraw from the clinical study or discontinue their participation at any time without any further obligation, penalty, or prejudice. If a subject withdraws from the study, the reason for withdrawal will be documented. If the withdrawal is a result of an adverse event, an Adverse Event Form must also be completed. Subjects who withdraw consent after treatment will not be required to undergo follow-up but will still be considered part of the subject cohort. In addition to withdrawing from the study voluntarily, subjects may also be withdrawn from the study by the investigative team, as necessary to ensure each subject's safety and welfare. Regardless of who initiates a given withdrawal, every attempt will be made to conduct an exit/final appointment prior to each subject withdrawal from the study. The reason for early discontinuation will be documented in the source documents and electronic case report forms (eCRFs). Data collected up to the time of study withdrawal will be included in the data analysis.

## **9.8 End of Study**

Subjects receiving the device may exit the study at the end of the study (i.e., the study is discontinued by the Sponsor) or when the subject has completed the final follow-up visit, whichever comes first, unless the subject opted to find an alternative treatment.

An End of Study CRF will be completed at the time the study is completed, discontinued, or lost to follow-up for each subject.

## 10 STATISTICAL CONSIDERATIONS

### 10.1 Primary Endpoint Hypothesis

The primary endpoint analysis consists of a one-sided test of the null hypothesis that no more than 60% of users are responders to the device against the alternative that more than 60% of users are responders, as given below:

$$H_0: R \leq 60\%$$

$$H_a: R > 60\%$$

Where,

R = % of users who are responders

In this study, R is estimated as the percent of subjects who are responders, and a subject will be considered a responder to the device if at least 80% of that subject's individual available PVR values are:

- a. Less than 50 mL OR
- b. Equal or less than baseline PVR with the subject's standard urinary management system

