### **8.5 Primary Endpoints**

#### **8.5.1 Primary Efficacy**

During each follow-up, and during the initial device insertion and evaluation, the Post-Void Residual (PVR) urine volume will be measured via ultrasound.

A subject will be considered a responder to the device if at least 80% of the subject's available PVR values are:

- a. Less than 50 mL OR
- b. Equal or less than baseline PVR with the standard urinary management system

If a subject drops out before the conclusion of the study after passing the Device Tolerability Screening, their PVR data will still be included in the primary analysis.

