### **8.8 Number of Sites and Sample Size**

Up to 4 sites in the United States are planned for this study.

The number of subjects to be enrolled in the study (ITT) as defined by EN ISO 14155; is 36 subjects. Of these, it is expected only 24 of the subjects will be found to meet the basic eligibility criteria to be tested for device tolerability screening.

Assuming a 33% dropout after the device tolerability screening, the final number of evaluable subjects required is a minimum of 16 subjects (See 10.1).

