## **9.3 Device Tolerability Screening**

During the Device Tolerability Screening, subjects will use the Connected Catheter to manage their chronic Urinary Retention. The duration of Tolerability Screening will be up to 7 days after the patient has had the first device inserted. The purpose of this screening is to ensure that the subjects can both tolerate the device and learn how to operate it properly. Any subject that experiences significant discomfort or cannot demonstrate proficiency in the operation of the device (or does not have a caretaker) will not proceed to the test phase of the study. Patients that are able to successfully use the device for up to 7 days and wish to continue the study will progress to the test phase. The data collection during the Device Tolerability Screening is identical to the data during the Test Phase. The subjects will be trained to manage his bladder using the Connected Catheter via the Controller on an intermittent voiding strategy. Instructions for Use (IFU) will be provided to the subject regarding how to properly use the Connected Catheter. The same assessments used in the Test Phase will be done at the end of the Device Tolerability Screening phase.

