### 10.2 Sample Size Justification

Based upon historical data and experience with the device, the estimate of R is expected to exceed 90% in this study. Limited descriptive statistical methods will be utilized to analyze data collected from this protocol. Although there will be limited power achieved with the number of patients completing this study, this data will provide a foundation for further clinical research with additional statistical rigor.

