### 10.3 Statistical Analysis

Data from all the sites will be pooled together assuming poolability analysis show that the data are poolable.

The primary efficacy endpoint will be hypothesis tested based on the mITT population. An analysis of all subjects that dropped out during or after the device tolerability screening will be provided.

The primary efficacy outcome will be assessed using an exact binomial test at the 0.05 significance level, in a one-sided test of the null hypothesis that the user responder rate is 0.60 or less, against the alternative hypothesis that the user responder rate is greater than 0.60.

For the primary safety endpoint, device related SAE will be analyzed with descriptive statistics and nominal 95% confidence intervals. Serious adverse events from all subjects that were treated with the investigational device will be included. Based on the sample size calculations, the source of the SAE will be from all 60 subjects that tested the device. There will be no formal statistical hypothesis testing.

Similarly, the secondary endpoints will be analyzed with descriptive statistics and nominal 95% confidence intervals.

Tipping point analyses will be conducted to investigate issues such as the possible impact of missing data.

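### The primary hypothesis is worded for all users, but the undefined mITT set appears to leave out men who fail the home tolerability week, so a rejection would support the claim only for men who pass it

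*Combined protocol and SAP*

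**What the plan says.** - **Claim.** Section 10.1 words its null as "no more than 60% of users are responders to the device against the alternative that more than 60% of users are responders" and defines the parameter as "R = % of users who are responders". Section 10.3 repeats the claim as a user responder rate.
- **Test.** Section 10.3 assesses it "using an exact binomial test at the 0.05 significance level, in a one-sided test", and states: "The primary efficacy endpoint will be hypothesis tested based on the mITT population". The term mITT is not defined there, in section 8 (which defines only ITT, as everyone who signs consent) or in the abbreviation list.
- **Tolerability week.** Under 9.2.7 and 9.3, men who meet the performance criteria at the insertion visit go home with the catheter in place for up to 7 days. "Any subject that experiences significant discomfort or cannot demonstrate proficiency in the operation of the device" is then kept out of the Test Phase. Section 8.2 also stops men who cannot or will not complete those days.
- **Who is retained.** The synopsis and 8.5.1 keep a man's PVR data in the primary analysis "If a subject drops out before the conclusion of the study after passing the Device Tolerability Screening". There is no matching rule for a man who fails that screening.
- **Numbers.** Section 8.8 expects 24 of 36 consented men to be tested for tolerability. It continues: "Assuming a 33% dropout after the device tolerability screening, the final number of evaluable subjects required is a minimum of 16 subjects". Section 10.2 adds that "the estimate of R is expected to exceed 90% in this study", and concedes limited power.
- **Other analyses.** Section 10.3 promises a separate analysis of men lost during or after tolerability screening, without a method, and tipping point analyses for issues such as missing data. For safety it refers to 60 subjects who tested the device.

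**The concern.** A man who wears the catheter at home for several days and stops because of discomfort, or because he cannot work it, is a user in the ordinary sense. He has PVR measurements and counts in the safety analysis. If he is not in the primary test, membership of the tested set depends on how the device performed in that man after treatment began. The responder rate then describes men already known to tolerate and operate the device, while the hypothesis speaks of users without restriction. At the planned loss of one third, the two rates can differ enough to put one above 60% and the other at or below it.

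**Working it through.** **Inputs.** Null rate 0.60 (10.1); exact binomial test, one-sided 0.05 (10.3); 24 men entering tolerability screening, 33% loss, 16 evaluable (8.8); expected responder rate 90% (10.2 says above 90%). I take 24 as the number discharged into the tolerability week.

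**Step 1: the plan's own figure.** 24 × (1 − 0.33) = 16.08, so 16 is reproduced. The plan states no power, so there is none to reproduce.

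**Step 2: who the 8 lost men are.** Section 8.8 places the loss after tolerability screening. But 8.5.1 keeps men who drop out after passing, so they would not reduce the evaluable number. The fall from 24 to 16 is coherent only if the 8 are lost at the tolerability stage and left out of the test. This is an inference; no sentence says it.

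**Step 3: the test in 16 men.** Tail probability: P(X ≥ r | n, p) = Σ C(n,k) p^k (1 − p)^(n−k), summed over k = r to n.
- P(X ≥ 13 | 16, 0.60) = 0.065, not significant.
- P(X ≥ 14 | 16, 0.60) = 0.018, significant. The smallest win is 14/16 = 87.5%.
- P(X ≥ 14 | 16, 0.90) = 0.789, the power at a true 90%.

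**Step 4: the same results over all 24, with the 8 lost men counted as non-responders.**

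| Responders | Rate in 24 | One-sided p |
|---|---|---|
| 14 (smallest win in 16) | 58.3% | 0.650 |
| 16 (every remaining man) | 66.7% | 0.328 |
| 18 | 75.0% | 0.096 |
| 19 (smallest win in 24) | 79.2% | 0.040 |

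The exact 95% interval for 14/24 is 36.6 to 77.9%. For 16/24 the one-sided 95% lower limit is 47.9%. A win in 24 allows 24 − 19 = 5 non-responders of any kind, against 8 lost. If two thirds pass and 90% of those respond, the all-treated rate is 2/3 × 0.90 = 0.60, exactly the null value, yet the 16-man test succeeds with probability 0.79.

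**Step 5: the other count of treated men.** With the 60 in 10.3 and the same one-third loss, the ceiling is 40/60 (p = 0.179). A win needs 43/60 (p = 0.041; 42 gives 0.072). The larger count does not change the answer under this scoring.

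**Step 6: the other scoring rule.** Sections 8.5.1 and 10.1 define a responder on available PVR values. Section 9.2.5 schedules three voiding cycles at the insertion visit, so men who fail the home week should have values.
- If all 16 remaining men respond, 16 + 3 = 19, so 3 responders among the 8 reach significance in 24.
- If 14 of the 16 respond, 14 + 5 = 19, so 5 of the 8 are needed.
- If all 24 are scored and respond at a true 90% (an assumption), P(X ≥ 19 | 24, 0.90) = 0.972.

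For the all-treated population, the planned test therefore runs from unreachable to very likely, depending on how these 8 men are scored.

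**The case against.** **The exclusion is not written down.** This is correct. Sections 9.7.1.1 and 9.7.1.5 say in general that data up to withdrawal are analysed, and 10.1 speaks of subjects with available PVR values. Those are general statements. The specific rule in 8.5.1 and the arithmetic in 8.8 point the other way, and neither set of passages settles what mITT means.

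**The endpoint is residual volume, not tolerability.** A man who stops for discomfort may well have emptied his bladder, and 9.2.7 lets him go home only after the voiding criteria are met. This stands. It defeats a stronger statement that a reader might infer, namely that a rate above 60% cannot be shown for all treated men even if every remaining man responds. That is true only if the lost men are counted as non-responders, and the plan contains no such rule. Even then, 16/24 exceeds 60% as a point estimate; what fails is the significance test.

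**Testing men who pass a run-in is legitimate.** Agreed. The filter is disclosed, and section 5 limits intended use to men who can operate the device or have trained caregivers. That covers proficiency failures, though not discomfort. The hypothesis must still name the population it describes.

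**Other analyses cover the gap.** The dropout analysis has no method or denominator and sits outside the test. The tipping point sentence does not say that it reaches men outside the analysis set. The concession on power in 10.2 does not address which population the claim concerns.

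**Conclusion.** The mismatch is real and should be fixed. The claim is worded for users, the test set is undefined, and on the most natural reading it holds only men who passed a week that depends on the device. A rejection would support the claim for those men alone.

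The size is conditional on two assumptions: that the fall from 24 to 16 is tolerability failure, and that those 8 men are non-responders. Under both, a win of 14/16 corresponds to 58.3% of treated men, and the ceiling of 66.7% does not reach significance. Drop the second assumption and the all-treated test can succeed. The documents therefore support saying that the all-treated conclusion depends on an unstated scoring rule. They do not support saying that it is unattainable, or that the plan expressly excludes these men. Since the remedy is mainly wording and the design itself can stand, this is a should-fix point rather than a fatal one.

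**What to change.** 1. Define mITT explicitly. If men who passed Device Tolerability Screening are intended, say so, and word R, both hypotheses and any conclusion for that population rather than for users.
2. Replace the unspecified dropout analysis in 10.3 with a pre-specified all-treated responder rate and exact 95% confidence interval. The denominator is every man discharged with the device into the tolerability week. Tolerability failures count as non-responders, with a sensitivity analysis scoring them on their available PVR values. Men who fail the same-day check before discharge are reported separately.
3. Reconcile the 60 treated subjects in 10.3 with the 24 in the synopsis and 8.8.

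The cost is protocol and SAP wording and one extra table; no subjects, visits or procedures are added. The drawback for the sponsor is a visibly lower all-treated rate: with non-responder scoring and 8 of 24 lost, 58.3% to 66.7% across the results that win in 16 men.

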### 10.2 Sample Size Justification

Based upon historical data and experience with the device, the estimate of R is expected to exceed 90% in this study. Limited descriptive statistical methods will be utilized to analyze data collected from this protocol. Although there will be limited power achieved with the number of patients completing this study, this data will provide a foundation for further clinical research with additional statistical rigor.

### 10.3 Statistical Analysis

Data from all the sites will be pooled together assuming poolability analysis show that the data are poolable.

The primary efficacy endpoint will be hypothesis tested based on the mITT population. An analysis of all subjects that dropped out during or after the device tolerability screening will be provided.

The primary efficacy outcome will be assessed using an exact binomial test at the 0.05 significance level, in a one-sided test of the null hypothesis that the user responder rate is 0.60 or less, against the alternative hypothesis that the user responder rate is greater than 0.60.

For the primary safety endpoint, device related SAE will be analyzed with descriptive statistics and nominal 95% confidence intervals. Serious adverse events from all subjects that were treated with the investigational device will be included. Based on the sample size calculations, the source of the SAE will be from all 60 subjects that tested the device. There will be no formal statistical hypothesis testing.

Similarly, the secondary endpoints will be analyzed with descriptive statistics and nominal 95% confidence intervals.

Tipping point analyses will be conducted to investigate issues such as the possible impact of missing data.

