## 8 CLINICAL STUDY DESIGN

The FREEDOM Study is a prospective, open, single-arm, non-significant risk (NSR) study to be performed in the United States with consecutive enrollment to evaluate the safety and efficacy of the Connected Catheter System in treating subjects with chronic Urinary Retention. All patients

that sign an informed consent form are considered to be part of the intended-to-treat (ITT) population.

The study will be broken up into 4 phases – Eligibility screening, Device Tolerability screening, Connected Catheter use, and Follow-Up. Figure 8-1 shows an overview of the study with the estimated sample size enrolled and treated.

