## 14.2 Subject Enrollment Process

All study candidates, after pre-screening, must appropriately consent to participate in the study, as administrated by qualified study site personnel using an IRB and Sponsor-approved informed consent form (ICF) prior to beginning any aspect of the study procedure or tests that are not standard of care for the site. Investigational sites will be required to document the consent process within each enrolled subject's medical record. Administering the questionnaires can be done prior to signing the ICF.

Only subjects who meet the inclusion/exclusion criteria, who signed the study enrollment informed consent will be considered enrolled in the study.

Timely communication by each site is critical to avoid over enrolling when the enrollment is close to the end of each phase.

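### Section 10.3 bases primary safety on 60 device-tested subjects, but the plan enrolls 36, expects about 24 to use the device, and prints no calculation that gives 60

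*Combined protocol and SAP*

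**What the plan says.** Section 10.3 analyses device-related SAEs descriptively, with nominal 95% confidence intervals and no hypothesis test. It first sets the rule: "Serious adverse events from all subjects that were treated with the investigational device will be included". The next sentence supplies a number and a source for it: "Based on the sample size calculations, the source of the SAE will be from all 60 subjects that tested the device".

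The planned numbers stand in section 8.8 and, in the same terms, in the synopsis: "The number of subjects to be enrolled in the study (ITT) as defined by EN ISO 14155; is 36 subjects". Fewer are foreseen to go on to use the device, since "it is expected only 24 of the subjects will be found to meet the basic eligibility criteria to be tested for device tolerability screening". Allowing for a further loss of 33%, section 8.8 then concludes that "the final number of evaluable subjects required is a minimum of 16 subjects".

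Two places define who is counted. Section 8 assigns to the ITT population all patients "that sign an informed consent form are considered to be part of the intended-to-treat (ITT) population". Section 14.2 uses a narrower idea of enrollment: "Only subjects who meet the inclusion/exclusion criteria, who signed the study enrollment informed consent will be considered enrolled in the study". Section 8 also says "Figure 8-1 shows an overview of the study with the estimated sample size enrolled and treated"; that figure is not visible in the text available for this review.

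**The concern.** Treated subjects are a subset of consented subjects. If 36 is the planned number who consent, no subset of it can supply 60 who tested the device. The sentence also credits sample size calculations, and section 10 prints none.

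The rate of device-related SAEs is the primary safety endpoint, and it has no test or success criterion. What the study can conclude about safety therefore depends on the width of an interval, and hence on the number treated. A reader of section 10.3 would expect a safety base well over twice the one that section 8.8 provides. An IRB or the safety monitor could not tell how many men are expected to be exposed to the device.

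**Working it through.** **Inputs.** 36 in the ITT population, 24 expected in tolerability screening, 33% dropout and at least 16 evaluable (synopsis and 8.8). 60 device-tested (10.3). Null responder rate 60% (10.1), expected rate above 90% (10.2), one-sided exact binomial test at 0.05 (10.3).

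**1. The plan's own flow.** 24 × (1 − 0.33) = 16.1, and 16 / (1 − 0.33) = 23.9, rounded up to 24. The sequence 36, 24, 16 is self-consistent, and 60 appears nowhere in it.

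**2. Ceiling on the number treated.** Under section 8, the ITT population is everyone who consents, so 36 is the ceiling. The narrower definition in 14.2 does not change this. Section 8.8 expects only 24 of its 36 to be eligible, so its 36 must be the consented count.

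**3. Expected number treated.** Sections 8.2 and 9.3 and Table 9-2 tie device use to tolerability screening, which gives about 24. This is an expectation, not a floor: section 9.2.1 describes the first insertion under the Eligibility Screening heading, so some subjects could be treated and go no further. The range is about 24 to at most 36.

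**4. Looking for a source of 60.** Section 10.1 holds only the hypothesis. Section 10.2 gives no sample size and concedes limited power. Elsewhere in section 10, the figure 60 occurs only as the 60% null rate. Taking 90% as the true rate, the stated test needs:

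| Power reached | n | Inflated, n / 0.67 |
|---|---|---|
| 84% | 14 | 21 |
| 92% | 17 | 26 |

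Neither is near 60. Sixty does arise from 40 / 0.67 = 59.7, rounded up, but the plan nowhere states 40 evaluable subjects. It also arises from 36 + 24, which counts the same men twice.

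**5. Size of the discrepancy.** 60 / 36 = 1.67 and 60 / 24 = 2.5.

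**6. Effect on the interval.** The plan names no interval method, so two are shown for zero events. The exact (Clopper-Pearson) two-sided 95% upper limit is 1 − 0.025^(1/n). The Wilson limit is z² / (n + z²) with z = 1.96. The one-event column is the exact upper limit.

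| n | Exact, 0 events | Wilson, 0 events | Exact, 1 event |
|---|---|---|---|
| 60 | 6.0% | 6.0% | 8.9% |
| 36 | 9.7% | 9.6% | 14.5% |
| 24 | 14.2% | 13.8% | 21.1% |

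**7. If 60 treated was intended.** At the plan's own pass rate of 24/36, 60 / (24/36) = 90 consented subjects are needed, 54 more than planned. If every consented subject were treated, 60 would be needed, 24 more than planned.

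**The case against.** The strongest reply is that little depends on the number. The sentence before it fixes the safety set as everyone treated, and that rule works whatever count follows. There is no safety test, no success criterion and no stated target for precision, so no decision in the plan uses 60. The precision loss shown above rests on illustrative event counts, not on a claim that the plan makes. All of this is fair. It limits the harm to a misstated plan, but it does not make the two figures compatible.

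It is also fair that only the contradiction is established, not which side is wrong. Figure 8-1 might show which count was intended, although it could not make both true. The 16 evaluable subjects are not a candidate safety denominator, since dropouts who used the device still count.

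The figure of 24 is open to question as well. Under section 9.2.7, subjects go home with the catheter only after meeting performance criteria in clinic, so a man may be treated and never start home use. The synopsis counts accessories as part of the investigational device, and the Catheter Assessment Tool is used at eligibility screening. On that reading, exposure could approach 36. Both points move the count between 24 and 36, and neither reaches 60. Finally, the lower end of the 60 to 90 range requires every consented subject to be treated, which the plan does not expect; 90 follows from its own pass rate.

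**Conclusion.** The concern holds. The 60 in section 10.3 cannot be reconciled with the 36, 24 and 16 in the synopsis and section 8.8, and the calculation it cites is not in the document. It exceeds the planned ceiling by 24 subjects and the expected number treated by 36. With no events, the study at its expected size could exclude device-related SAE rates above about 14%, not above about 6%.

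This assumes that the 36 in section 8.8 is the consented count, as section 8 and the eligibility expectation both imply, and that about 24 is an expectation that could rise toward 36. The percentages assume zero events and a two-sided 95% interval; the choice between exact and Wilson hardly matters. The final analysis would still use the number actually treated, so the defect lies in the stated safety sample size and its implied precision, not in bias.

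**What to change.** Reconcile section 10.3 with section 8.8 and the synopsis, and check Figure 8-1 against whichever count is kept.

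- **If 36 stands:** replace the sentence containing 60 with one such as: *SAEs will be summarised for every subject treated, counted from first insertion; about 24 are expected, and at most the 36 planned.* Name the interval method and give the matching zero-event upper limit (exact: about 14% at 24, about 10% at 36). If contact with the Catheter Assessment Tool alone is meant to count as treatment, say so. The cost is one sentence and a figure check. No patients are added, and the stated safety precision becomes less favourable.
- **If 60 treated was intended:** correct the enrollment figures in the synopsis and section 8.8, and print the calculation that gives 60. Planned consented subjects would rise from 36 to between 60 and 90, depending on how many are treated before eligibility is settled.
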